8.5.2 Dose escalation Part A (SAD)

The dose will be increased such that the predicted plasma concentrations in any subject (C_{max} and AUC) after the top dose do not exceed the following limits, which are based on the NOAEL in the most sensitive species (dog).

C_{max}: 4,710 ng/mL	AUC_{last}: 24,500 ng.h/mL
--	--

Dose escalation in Cohorts A1–A4 is complete. The planned dose for A5 is 100 mg.

Three further intermediate or higher dose levels may be explored in the optional groups of subjects (Groups A6–A8).

The maximum dose in Part A will not exceed 140 mg. The predicted plasma concentrations in any subject at the maximum dose (140 mg) are predicted to be 3-fold and 4-fold below the C_{max} and AUC limits above, respectively. The predicted plasma concentrations and rationale for the maximum dose (140 mg) are provided in section 6.5.2.

The trial will be stopped if the criteria in section 8.4.1 are met.

8.5.3 Dose selection Part B (food effect)

Part B will not proceed until the SRG has reviewed safety, tolerability (up to 48 h after dosing), and PK data (up to 24 h after dosing) from at least 3 groups in Part A, as described in section 8.5.1.

The dose selected for Group B1 will be no higher than 50% of the highest dose tested in Part A that caused no safety concerns.

If Group B2 is required, it will proceed once the SRG has reviewed safety and tolerability (up to 48 h), and PK data from at least 4 subjects in Group B1, up to 24 h

after dosing in each treatment session, and available data from Part A. The dose selected for Group B2 will be the same or lower than one that has been given in Part A without any safety concerns.

8.5.4 Dose escalation Part C (MAD)

Part C may start before the completion of Part A. At a minimum, Part C will not proceed until the SRG has reviewed safety and tolerability (up to 48 h), and PK data (up to 24 h after dosing) from at least 3 groups in Part A, as described in section 8.5.1.

The dose, dosing regimen (once or twice daily), and whether the dose is taken fed or fasted, will be determined by the SRG based on review of available safety, tolerability, and PK data from Parts A and B and previous cohorts in Part C.

Dose selected for Group C1: The first total daily dose (ie, morning plus evening dose, if a twice-daily dosing regimen is chosen) selected for Part C (Group C1) will be the same as, or lower than, a single dose that has been given in Part A without any safety concerns. Additionally, to account for possible accumulation, at the proposed first dose level the predicted C_{max} and AUC_{tau} (at steady state) in any individual subject must not exceed the maximum observed C_{max} and AUC_{inf} achieved so far in Part A.

Doses selected for Groups C2–C3 and optional group C4: It is expected that the dose level tested will increase in each new group. However, the dose will be increased only if, at the new proposed dose level, C_{max} and AUC_{tau} (at steady state) in any individual subject are not predicted to exceed the maximum observed C_{max} and AUC_{inf} achieved following a single dose in Part A that caused no safety concerns.

The daily dose will be increased such that it does not exceed 3.5 times the highest daily dose previously tested in Part C that was safe and well tolerated. Dosing will be discontinued if the criteria in section 8.4.1 are met.

8.5.5 Repeating a dose level or selection of a lower dose level (Parts A and C)

In Parts A and C, the SRG may decide to test a lower dose level of BEN8744, or to repeat a dose level, provided it does not meet the criteria in section 8.4. Such decisions will be made and documented in line with HMR SOPs.

A dose level may be repeated under the following circumstances.

- If it was safe and well tolerated, and resulted in BEN8744 plasma concentrations within the limit (section 8.5.2).
- If AEs occurred that caused mild or moderate discomfort, but did not in any way threaten the health of the subject, that dose level may be repeated with the aim of exploring further the relationship between dose and AE. If, in the SRG's judgement, it would be unreasonable to expose further subjects to the level of

discomfort experienced by the subjects who have already received the dose, a lower dose may be tested. The selected dose will be either a lower dose level that has already been given, or an intermediate level that has not previously been given; in either case, the aim is to learn more about the relationship between AEs and dose (or plasma concentration) of BEN8744.

9 Trial population

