After single doses of 2–60 mg, BEN8744 demonstrated a shorter than expected elimination half-life, ranging approximately 2–4 h. At the highest dose tested (60 mg), mean C_{avg} was below IC_{90} . However, a single subject had a higher AUC_{inf} , approximately 2-fold above the mean and above IC_{90} . In all subjects after 60 mg BEN8744, plasma concentrations decreased below the IC_{50} by 11 h postdose. Considering the observed short half-life, and predicted required time above IC_{50} for efficacy in patients, a twice daily dosage regimen will be required in Part C (MAD Phase) to achieve exposures above IC_{50} for up to 18–24 h.

The impact of gut P-glycoprotein (P-gp) efflux and gut cytochrome p450 3A4 (CYP3A4) mediated metabolism was not expected to be significant in humans; however, emerging clinical data suggests there is an impact which is significant at lower doses. Between 2 and 6 mg QD the increase in PK parameters appeared dose-proportional, but escalation between 6, 20 and 60 mg QD resulted in a greater than proportional increase in AUC_{inf} , suggestive of non-linear PK. Additionally, between-subject variation was high. While the linear approach overpredicted exposures at low doses, the mean C_{max} and AUC_{inf} at 60 mg aligns with predicted exposures. Mean apparent clearance (CL/F) decreased with an increase in dose from 6 to 60 mg QD, which may indicate approaching saturation of gut P-gp and CYP3A4. Hence, at higher doses exposure is expected to be closer to dose-proportional.

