8.1.3 Part C

Enrolment of up to 32 healthy subjects is planned, in up to 3 groups (Groups C1–C3) and 1 optional group (Group C4). Each group will consist of 8 subjects.

Each subject will receive daily doses of BEN8744 or placebo, by mouth, for 14 days. At each dose level, 6 subjects will receive BEN8744 and 2 will receive matching placebo. Doses will be taken once or twice daily in the fasted state, unless emerging data indicate they should be taken in the fed state.

[figure not shown]
Part C will not start until at least 3 dose levels have been completed in Part A, as described in section 8.5.4. Part C may also be conducted in parallel with Part B. The dose, dosing regimen (once or twice daily), and whether the dose is taken fed or fasted, will be determined based on review of the available safety, tolerability and PK results from Parts A and B, and previous groups in Part C, as described in section 8.5.

The first total daily dose (ie, morning plus evening dose, if a twice-daily dosing regimen is chosen) tested in Part C (Group C1) will be the same as, or lower than, a single dose that has been given in Part A without any safety concerns. See also section 8.5.

[figure not shown]
[figure not shown]
[figure not shown]
Subjects will be screened within 28 days before their first dose of trial medication. Subjects will be resident on ward from the day before their dose (Day -1) until up to 72 h after their final dose (Day 17). They will return for a follow-up visit 7 (± 2) days after their inpatient stay (Day 24 ± 2 days).

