8.4 Stopping criteria

8.4.1 *Trial stopping criteria*

The trial will be stopped if either of the following occurs:

- 1 or more SAEs considered to be at least possibly related to study treatment; or
- 2 or more severe or clinically significant adverse events (AEs) that are considered to be at least possibly related to study treatment at any dose level.

In Parts A and C, treatment allocations may be unblinded to aid safety review, provided that the unblinding is appropriately documented. In Part B, all subjects will receive BEN8744.

If, after an internal safety review, it is appropriate to restart the trial, a substantial amendment will be submitted to the MHRA and research ethics committee (REC). The trial will not restart until the amendment has been approved by the MHRA and REC.

8.4.2 *Dose escalation stopping criteria*

A dose level will not be repeated, or exceeded, if:

- the results of safety tests for that dose level give the sponsor or investigator cause for concern,
- the investigator or sponsor considers that dose level to be poorly tolerated.

In addition, a dose level will not be exceeded if:

- plasma concentrations at higher doses in any individual subject are predicted to exceed the exposure threshold (see section 8.5).
- 1 or more Hy's Law cases; Hy's Law is defined as alanine aminotransferase (ALT) and/or aspartate aminotransferase (AST) elevations $\geq 3 \times$ upper limit of normal (ULN) in the presence of a total bilirubin increase $\geq 2 \times$ ULN in the absence of other findings of cholestasis such as a significant increase in alkaline phosphatase (ALP) and without an alternative diagnosis that could explain the increase in ALT/AST and bilirubin.

- 2 or more subjects have a mean QTcF of > 500 msec or increase from baseline of > 60 msec

The trial will be stopped if any criterion in section 8.4.1 is met.

Dosing will be discontinued in an individual subject if any criterion in section 9.4.2 is met.

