8.5 Criteria for dose selection

8.5.1 **Review of data by the Safety Review Group**

During the study, the dose will be increased only if the safety, tolerability, and PK of the previous dose are acceptable.

All doses will be selected by the Safety Review Group (SRG), which will include (as a minimum) the principal investigator (or delegate) and the sponsor's medically qualified representative (or delegate). Each dose decision will be made and documented in line with HMR standard operating procedures (SOPs).

Before selecting a new dose level (for any group), the SRG will review, as a minimum, the safety, tolerability, and PK data from the previous dose level and (if different) the highest dose level tested to date, as described below. Safety, tolerability, and PK data obtained from the previous group(s) will also be reviewed, if applicable. All data used to support dose selection will be quality checked.

Review of safety and tolerability data

The SRG will review (as a minimum) safety and tolerability data, up to 48 h after final dosing, from at least 4 evaluable subjects who have received active treatment at the highest dose level tested to date. An evaluable subject is one who completes dosing and has undergone procedures until 24 h after final dosing, and had no major protocol deviations. To maintain blinding, data from at least 6 of the 8 subjects in each group must be reviewed to ensure that the dataset includes at least 4 evaluable subjects on active treatment. If fewer subjects than planned are dosed, any subjects required to complete the group may be dosed in parallel with subsequent groups.

The safety data reviewed will include, as a minimum:

- AEs and SAEs, including description, frequency, intensity, onset, duration, and relationship to treatment
- physical examinations
- vital signs
- 12-lead safety ECG
- telemetry (Part A)
- laboratory safety tests

- C-SSRS (Part C)

Review of pharmacokinetic data

The SRG will review (as a minimum) PK data up to at least 24 h after final dosing from at least 4 evaluable subjects on active treatment at the highest dose level tested to date before the dose is escalated.

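### In 8.5.4 the exposure ceiling for Group C1 may be set by a Part A dose that raised a safety concern; the ceiling for Groups C2–C4 may not

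*Combined protocol and SAP*

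**What the plan says.** Section 8.5.4 sets two conditions for Group C1:

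- **Dose.** The total daily dose may not exceed "a single dose that has been given in Part A without any safety concerns". Section 8.1.3 repeats this.
- **Exposure.** The paragraph continues "Additionally, to account for possible accumulation" and requires that predicted steady-state Cmax and AUCtau "in any individual subject must not exceed the maximum observed C_{max} and AUC_{inf} achieved so far in Part A".

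For Groups C2–C4 the exposure ceiling is the maximum Cmax and AUCinf "achieved following a single dose in Part A that caused no safety concerns". Their daily dose is otherwise limited only by a 3.5-fold step from the highest well-tolerated Part C daily dose.

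Section 8.4.2 bars repeating or exceeding a dose level if "the results of safety tests for that dose level give the sponsor or investigator cause for concern", or if it is poorly tolerated. Section 8.4.1 stops the whole trial only for a possibly related SAE, or for two or more possibly related severe or clinically significant AEs. Under 8.5.1 the Safety Review Group (SRG) must review "the safety, tolerability, and PK data from the previous dose level and (if different) the highest dose level tested to date" before choosing a dose.

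**The concern.** A Part A dose can raise a concern under 8.4.2 without triggering 8.4.1. That dose level is then closed, but its Cmax and AUCinf still count as exposures reached in Part A, and so can still set the C1 ceiling. They could not set the C2–C4 ceiling.

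The pattern suggests an omission. The B1 dose, the B2 dose, the C1 dose and the C2–C4 exposure ceiling all carry the no-concern condition; the C1 exposure ceiling alone does not, and no reason is given. C1 is the first group dosed for 14 days, and Table 8 gives Part C no sentinel subjects.

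The dose cap limits milligrams, not exposure per milligram. Part A is fasted, but 8.1.3 says of Part C: "Doses will be taken once or twice daily in the fasted state, unless emerging data indicate they should be taken in the fed state". Section 11 places evening doses about 1 h after dinner, and Part C may run alongside Part B, so the food effect may not be known when C1 is chosen.

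**Working it through.** Call a Part A dose *clean* if it caused no safety concern. Let *r* be predicted exposure per mg in Part C relative to fasted Part A.

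**Inputs.** Table 2, highest subject at 60 mg: Cmax 688 ng/mL, AUCinf 2,390 ng·h/mL. Table 2 predictions: 1,100 and 3,986 at 100 mg; 1,541 and 5,581 at 140 mg. Table 4, 50 mg BID, highest prediction: Cmax 550.21, AUC24 4,063.33. Section 6.2.4 reports "a shorter than expected elimination half-life, ranging approximately 2–4 h".

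**Reproducing the plan's figures.** Scaling the 60 mg maximum linearly gives AUCinf 2,390 × 100/60 = 3,983 at 100 mg (plan 3,986) and 2,390 × 140/60 = 5,577 at 140 mg (plan 5,581). For Cmax it gives 688 × 100/60 = 1,147 (plan 1,100). The stated 3- and 4-fold margins at 140 mg hold: 4,710/1,541 = 3.06 and 24,500/5,530 = 4.43.

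**Accumulation.** Under linear superposition the ratio is 1/(1 − 2^(−tau/t½)), applied to Cmax; steady-state AUCtau equals single-dose AUCinf at the same dose.

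- tau 24 h: 1.0002 (t½ 2 h) to 1.0159 (t½ 4 h)
- tau 12 h: 1.0159 to 1.1429

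**Limit on r.** Each rule passes a regimen up to r = min(Cmax ceiling/Cmax, AUC ceiling/AUCtau). The rules disagree between the two limits.

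**Illustration 1: 60 mg clean, 100 mg not, with 100 mg exposures as predicted.** The ceilings are 688 and 2,390 (C2–C4 wording) against 1,100 and 3,986 (C1 wording): 1,100/688 = 1.60 and 3,986/2,390 = 1.67.

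**Illustration 2: 100 mg clean, 140 mg not, with both as predicted.** The ceilings are 1,100 and 3,986 against 1,541 and 5,581: 1,541/1,100 = 1.40 and 5,581/3,986 = 1.40.

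| Case | C1 regimen | Steady-state Cmax | AUCtau | r limit, C2–C4 wording | r limit, C1 wording |
|---|---|---|---|---|---|
| 1 | 60 mg once daily | 688.2–698.9 | 2,390 | 1.00–0.98 | 1.60–1.57 |
| 1 | 30 mg BID | 349.5–393.1 | 1,195 | 1.97–1.75 | 3.15–2.80 |
| 2 | 100 mg once daily | 1,100.3–1,117.5 | 3,986 | 1.00–0.98 | 1.40–1.38 |
| 2 | 50 mg BID (formula) | 558.7–628.6 | 1,993 | 1.97–1.75 | 2.76–2.45 |
| 2 | 50 mg BID (Table 4) | 550.21 | 4,063.33/2 = 2,031.7 | 1.96 | 2.75 |

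For the Table 4 row, AUC sets both limits: 3,986/2,031.7 = 1.96 and 5,581/2,031.7 = 2.75.

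At r = 1, BID dosing sits at about 50–57% of the clean ceiling in both cases, so both rules clear it. Once-daily dosing at the full clean dose reaches the clean ceiling at r = 1 and exceeds it by at most about 1.6%, on Cmax.

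**The case against.** The strongest reply is structural. C1's daily dose is itself tied to a clean Part A dose, whereas C2–C4 have only the 3.5-fold step. The no-concern condition thus appears once in each rule: on dose for C1, on exposure for the later groups. On that reading the C1 ceiling is only an extra check for accumulation, and accumulation is small.

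Three further points limit the effect:

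- Escalation to 100 mg under 8.4.2 implies that 60 mg raised no concern, so the two ceilings probably coincide today. This is an inference, because the Cohort A1–A4 adverse-event table (Table 1) was not in the text available for this check.
- Section 6.2.4 expects twice-daily dosing, and C1 may start low. At 20 mg BID (Table 4: Cmax 57.36, AUC24 488.12, so about 244 per 12 h), the rules would first disagree at r = min(688/57.36, 2,390/244.06) = min(12.0, 9.8) = 9.8. Exposure rose more than proportionally from 6 to 60 mg, so splitting a dose may also lower exposure per mg.
- The SRG would know of any concern and is unlikely to rely on those exposures.

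All of this limits the consequence; none of it supplies the missing condition. A milligram cap does not bound exposure if C1 is dosed fed or after dinner. Group A5 and optional Groups A6–A8 are still to come. The SRG would be equally aware for C2–C4, yet the condition was written there.

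**Conclusion.** The concern holds and is minor. The C1 ceiling lacks a condition that the C2–C4 ceiling carries, and nothing in 8.1.3, 8.4.1, 8.4.2, 8.5.1 or 8.5.5 adds it.

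Two things must both happen for it to change a decision: a higher-exposure Part A dose raises a concern, short of stopping the trial, before C1 is chosen; and predicted C1 exposure falls above the clean maximum but within the overall one. Nothing in the available text reports the first. In the illustrations the C1 ceiling is 1.40- to 1.67-fold looser. For BID dosing at the full capped daily dose the rules part only once exposure per mg rises by about 1.75- to 1.97-fold; for once-daily dosing at that dose they part at r of about 0.98–1.00.

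These figures assume linear superposition, a half-life of 2–4 h, and 100 and 140 mg exposures equal to the Table 2 predictions. The documents give no size for the food effect, so the likelihood of reaching those values of r cannot be judged.

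**What to change.** In 8.5.4, limit the C1 ceiling to the maximum observed Cmax and AUCinf so far "achieved following a single dose in Part A that caused no safety concerns". The background restatement in 6.5, which also omits the condition, could be matched but need not be.

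The cost is one phrase. If every Part A dose is clean, no decision changes. If one is not, C1 loses only exposure headroom that C2–C4 are already denied.

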6.5 Rationale for choice of dose(s)

At the time of writing, Cohorts A1–A4 (Part A) have completed the study (see section 6.2.4 for details). After a single 60 mg dose (Cohort A4), 1 subject met 89% of the protocol-defined AUC_{inf} threshold (based on IC_{90} predicted *ex vivo* data). The protocol (section 8.5.4) states that doses in Part C (MAD) cannot be predicted to exceed the maximum observed C_{max} and AUC_{inf} achieved in Part A (SAD). Due to the PK profile and indication-specific tissue exposure requirements, further dose

escalation in Part A up to a maximum of 140 mg QD may be required to support the MAD phase of the study, and future studies of BEN8744. So, the protocol has been subject to a substantial amendment, incorporating data from completed Cohorts A1–A4, to provide rationale to allow dosing up to 140 mg QD in Part A (which is expected to exceed the previous threshold but remain within the updated PK threshold: the NOAEL in the most sensitive species [dog]).

6.5.1 *Doses up to Cohort A4*

Before the present study (BB-8744-1001), BEN8744 had not yet been administered to humans, so no human exposure data existed. However, PDE10 inhibition as a mechanism of action has been described in humans, with numerous molecules under development as therapeutic agents. Two such examples are Mardepodect and Balipodect, both of which have completed clinical trials. The most frequently reported adverse effects from acute dosing of both agents is somnolence, which is often reported in a dose-dependent manner and is attributed to on-target activity of PDE10A inhibition in the brain when receptor occupancy exceeds 20%. This effect has also been seen in other preclinical species.

Based on *in vitro* potency and prediction of human PK from animal studies, it was calculated that a starting dose of 2 mg for BEN8744 was predicted to have < 1% PDE10A enzyme occupancy in the brain and about 20% average enzyme occupancy in the periphery. At this low dose on BEN8744, any potential side effects (ie sedation) are minimised (in contrast to other PDE10A inhibitors where uptake into the brain is about 10-fold higher than that predicted for BEN8744). The exposure level at this dose was predicted to be > 690-fold below levels where sedation occurs in pre-clinical animals.

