	Human dose	Predicted % receptor occupancy C_{avg} (plasma)	C_{max} (ng/ml)	AUC_{24} (ng.h/ml)	Safety margin C_{max}	Safety margin AUC_{24}
Starting dose	2 mg QD	19	6.6	48	714	510
PAD	10 mg QD	56	75	261	63	94
MRSD	38 mg QD	82	346	936	14	26
Top dose	140 mg QD	90	1,190	2,674	4	9
HED	380 mg QD	98	3,704	9,794	1	3

Abbreviations: HED = human equivalent dose; MRSD = maximum recommended starting dose; PAD = pharmacodynamically active dose; QD = once-daily; C_{max} = maximum plasma concentration; C_{avg} = average plasma concentration during multiple-dose administration; AUC_{24} = area under the concentration–time curve from time zero to time 24 h.

Safety margins are calculated based on the NOAEL in the dog (5 mg/kg BID) from a 28-day toxicity data (Report CRL-522041); Dog NOAEL 10mg/kg/day. HED calculated by multiplying mg/kg/day by appropriate conversion factor (0.54 for dogs) to obtain the HED in mg/kg, and multiply by body weight, based on 70 kg human. MRSD calculated using a 10-fold safety margin from the HED. PK dose simulations and receptor occupancy calculations for doses reported in 22-8744-005PK.

Anticipated human pharmacologically active dose range

Before the start of this study, PAD doses were predicted based on the target unbound average plasma concentrations ($C_{average}$) of 0.7 to 7.0 nM (the IC₅₀–IC₉₀ of BEN8744) after BID dosing of BEN8744 for 14 days. Considering the variability in the model predictions, a dose range was predicted to be 5–12 mg BID and 46–69 mg BID based on $C_{average,u}$ for free IC₅₀ and IC₉₀ levels, respectively, in humans. These dose

estimations are theoretical, based on *in vitro* IC₅₀, plasma protein binding, and predicted PK in humans. A single dose of 10 mg BEN8744 was predicted to provide about 50% enzyme occupancy in the periphery. The highest planned dose in this study is 140 mg, which is predicted to achieve the theoretical IC₉₀ C_{average,u}. Dose levels may change (upwards or downwards) depending on observed human exposure, but no dose will exceed 140 mg/day.

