6.5.2 Subsequent dose levels

Based on the observed PK profile so far, and the relationship between PDE10 theoretical target engagement and BEN8744 concentrations seen in this study to date, it is predicted that due to the short half-life of BEN8744 (~2–4 h) an estimated daily dose of approximately 100 mg (50 mg BID) will be required to maintain sufficient target engagement in all target tissues over a 24 h period in future studies.

The maximum planned dose for Part A (140 mg QD), is predicted to achieve an absolute maximum blood concentration of C_{max} = 1,541 ng/mL, AUC₂₄ = 5,530 ng*h/mL, and AUC_{inf} = 5,581 ng*h/mL (see Table 2). That is 3- and 4-fold below the NOAEL in the 28-day dog study for C_{max} and AUC, respectively, and will not be exceeded in any 24 h period. The planned dose for Cohort A5 is 100 mg QD. Planned doses for Parts B and C may be adjusted to account for differences between predicted and actual/observed PK, in line with the dose escalation criteria in section 8.5.

[figure not shown]
Based on non-parametric superposition modelling (see Table 4), using data from the subject with the highest exposure to date (Cohort A4 [60 mg]), it is anticipated that the BEN8744 pharmacologically active dose will be ~ 50 mg BID. As shown in Figure 3, the 50 mg BID dose is expected to achieve a time (T) > IC₅₀ of 18 (mean) to 24 h (maximum) with a C_{trough}/IC₅₀ ratio of approximately 1. In order to proceed with Part C (MAD) dosing at > 30 mg BID, the limit in section 8.5.2 has been updated to the NOAEL in the most sensitive species (dog), to allow dosing up to 140 mg to achieve the T > IC₅₀ and C_{trough}/IC₅₀ ratio predicted to achieve the required efficacy for BEN8744.

Table 4: Predicted BEN8744 plasma pharmacokinetic parameters (maximum and mean) following BID administration at 20 and 50 mg

Cohort/Dose (BID)*	C_{max} (ng/mL)	AUC_{24} (h*ng/mL)	$T > IC_{50}$ (h)	C_{trough}/IC_{50} Ratio	Margin to dog NOAEL (C_{max}/AUC)
20 mg Observed	57.36 (mean 42)	488.12 (mean 320)	11.57 (mean 10)	0.17	82/50
50 mg Predicted	550.21 (mean 264)	4,063.33 (mean 1,744)	24.53 (mean 18)	1.06	9/6

BID: twice-daily; C_{max} : maximum plasma concentration; AUC: area under the concentration–time curve; AUC_{24} : AUC from time 0 to 24 h; IC_{50} : concentration required for 50% inhibition; C_{trough} : trough plasma concentration. NOAEL: no observed adverse effect level; T = time.

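### Under twice-daily dosing, the section 8.5.4 cap for Groups C2–C4 limits AUC per 12-h interval and not per day, although sections 6.5 and 6.5.2 reason per day

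*Combined protocol and SAP*

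**What the plan says.** Section 8.5.4 sets the exposure test for Groups C2–C4: the dose rises only if "C_{max} and AUC_{tau} (at steady state) in any individual subject are not predicted to exceed the maximum observed C_{max} and AUC_{inf} achieved" after a single Part A dose that raised no safety concern. Section 16.1.1 defines AUCtau as the AUC over one dosing interval. Section 10.6 puts twice-daily doses 12 h apart, and section 6.2.4 expects Part C to need that regimen.

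Group C1 has an extra daily rule. It governs "The first total daily dose (ie, morning plus evening dose, if a twice-daily dosing regimen is chosen) selected for Part C (Group C1"), which may not be above a single dose given in Part A without safety concerns. This is not repeated for C2–C4.

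Three other limits on daily dose or exposure apply to C2–C4:

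- the step limit in 8.5.4: "The daily dose will be increased such that it does not exceed 3.5 times the highest daily dose previously tested in Part C";
- the ceiling in 6.5.1: "no dose will exceed 140 mg/day";
- the statement in 6.5.2 that the predicted 140 mg exposure (AUC24 5,530 ng*h/mL) "will not be exceeded in any 24 h period".

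On timing, 8.5.4 says "Part C may start before the completion of Part A". Section 6.5 reports that 8.5.4 "states that doses in Part C (MAD) cannot be predicted to exceed the maximum observed C_{max} and AUC_{inf} achieved in Part A (SAD") and that further "escalation in Part A up to a maximum of 140 mg QD may be required to support the MAD phase of the study". Section 6.5.2 links the raised Part A limit to dosing above 30 mg BID in Part C.

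**The concern.** Section 8.5.4 ties repeated-dose exposure to exposure already seen after single doses in a first-in-human trial. Under BID dosing, one side of its AUC comparison covers 12 h. The other side is in effect a full day: the largest 60 mg AUC24 is 2,380 and the largest AUCinf is 2,390 ng*h/mL. A dose can pass while the two daily intervals together exceed anything observed in Part A.

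The rationale sections rely on more than that. Section 6.5 cites the cap when it says that more Part A escalation may be needed to support Part C, and 6.5.2 places the constraint just above 30 mg BID, which is 60 mg a day. As worded, the cap does not bind there. What is at stake is whether the written rule delivers the Part A support that the rationale describes.

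**Working it through.** **Inputs.** Table 2, 60 mg maxima: Cmax 688 ng/mL, AUCinf 2,390 ng*h/mL. Table 2, predicted maxima at 100 mg: Cmax 1,100, AUCinf 3,986; at 140 mg: AUC24 5,530, AUCinf 5,581. Table 4, 50 mg BID, highest subject: Cmax 550.21, AUC24 4,063.33. Section 8.5.2 limits (dog NOAEL): Cmax 4,710, AUC 24,500. Half-life 2–4 h (6.2.4).

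**1. The plan's own figures reproduce.** Margins at 50 mg BID: 4,710/550.21 = 8.6 and 24,500/4,063.33 = 6.0 (stated 9/6). Linear scaling of the highest 60 mg AUCinf: 2,390 × 100/60 = 3,983 (stated 3,986) and 2,390 × 140/60 = 5,577 (stated 5,581). The Table 4 AUC margin uses the 24-h AUC.

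**2. 50 mg BID on 60 mg data.** Take C1 at 20 mg BID and the next group at 50 mg BID, the two regimens in Table 4. Assuming equal intervals, AUCtau = 4,063.33/2 = 2,032.

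| Limit | Value | Allowed | Result |
|---|---|---|---|
| C1 daily dose | 40 mg | 60 mg | pass |
| Step in daily dose | 100/40 = 2.5 | 3.5 | pass |
| AUCtau | 2,032 | 2,390 | pass |
| Cmax | 550 | 688 | pass |
| Daily dose | 100 mg | 140 mg | pass |
| 24-h AUC | 4,063 | 5,530 | pass |

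Scaling the 688 directly and adding carry-over, with R = 1/(1 − 2^(−12/t½)) = 1.016 (2 h) to 1.143 (4 h), gives Cmax = 688 × 50/60 × R = 582 to 655, still below 688.

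Daily exposure against the observed maximum: 4,063.33/2,390 = **1.70**.

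**3. Sensitivity to linearity.** Section 6.2.4 reports a more than proportional rise from 6 to 60 mg. As an assumption, fit a power model to the Table 2 mean AUCinf at 20 and 60 mg: exponent = ln(1,059.2/164.12)/ln(60/20) = 1.70. The highest subject at 50 mg is then 2,390 × (50/60)^1.70 ≈ 1,754 per dose, or 3,508 per day without carry-over. The ratio is 3,508/2,390 = **1.47**.

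**4. Where each version of the cap binds on 60 mg data (linear).**

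- As written, Cmax: 60/R = 59.1 to 52.5 mg BID.
- As written, AUCtau: 2,390/(4,063.33/100) = 58.8 mg BID. Together with Cmax, the cap admits about 52–59 mg BID.
- On a 24-h basis: 2,390/(4,063.33/50) = 29.4 mg BID, or 60/2 = 30 mg BID by dose.

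Only a daily basis gives the 30 mg BID in section 6.5.2.

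**5. After A5 at its predicted maximum.** 4,063.33/3,986 = **1.02** (linear); 3,508/3,986 = **0.88** (power model for the 50 mg dose). A 24-h cap would then admit 3,986/(4,063.33/50) = 49.0, or 3,986/(2 × 2,390/60) = 50.0 mg BID. As written, the cap admits about 84–98 mg BID: Cmax limit 1,100/(688/60 × R) = 94.4 to 83.9; AUCtau limit 3,986/(4,063.33/100) = 98.1. The 6.5.2 ceiling binds first, at 5,530/(4,063.33/50) = 68.0 or 5,530/(2 × 2,390/60) = 69.4 mg BID, which is 5,530/3,986 = 1.39 times the A5 maximum. If Part A reaches its predicted 140 mg maximum, the gap closes: 5,530/5,581 = 0.99.

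**The case against.** The comparison is a standard accumulation check. Under linear kinetics, steady-state AUCtau equals single-dose AUCinf, so the rule is coherent per dose. This stands; the point is what the rule leaves uncovered.

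The excess above 1.02 at 50 mg BID needs an order that no text plans. Before C2, the Safety Review Group needs C1 data to 48 h after the last of 14 days of dosing. A5 is a single dose with the same 48-h review, and it is the next planned cohort. This also stands, and it limits the weight of the point.

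The 30 mg BID figure does not prove that the sponsor read the C2–C4 cap as a 24-h cap. The C1 rule gives the same figure (60 mg a day), and 6.5.2 names the 8.5.2 limit, not 8.5.4, as the one updated. That is fair. But the C1 route is also a daily basis, and it does not bind C2–C4, so the mismatch remains on either explanation.

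A reader might infer that daily exposure in C2–C4 is unlimited or that the toxicology limit is at risk. The documents support neither. The 3.5-fold step, 140 mg/day, the 24-h ceiling and the individual exposure threshold in 8.4.2 all apply. Even at the 24-h ceiling the AUC margin is 24,500/5,530 = 4.4. Safety Review Group review and the stopping rules also apply.

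**Conclusion.** The point holds, at moderate weight. For C2–C4 under BID dosing, 8.5.4 controls exposure per dose and not per day, and so does not do what 6.5 and 6.5.2 rely on. With the Part A maximum at 60 mg, 50 mg BID would pass every written limit at about 1.5 to 1.7 times the largest observed AUCinf. After A5 at its predicted maximum, the ratio is about 0.9 to 1.02. The NOAEL margin for AUC at 50 mg BID is about 6-fold.

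These figures assume that 60 mg caused no safety concerns (the Part A adverse event table is not in the supplied text), that the two 12-h intervals are equal, and that the Table 4 predictions are close to steady state. Evening doses follow dinner (section 11), so a food effect could move them either way. A reader might take 1.70 as the exposure the trial will produce. It is the linear-scaling end of a range, in a sequence the text permits but does not plan.

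**What to change.** In 8.5.4, for all Part C groups, require that predicted steady-state AUC0-24 (morning plus evening intervals under BID) and Cmax in any individual subject do not exceed the maximum AUCinf and Cmax observed in Part A. At minimum, extend the C1 rule to C2–C4, so that the total daily dose is no higher than a Part A single dose without safety concerns. In either case, restate in 8.5.4 the 140 mg/day and 24-h exposure ceilings that now appear only under 6.5.

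This is an amendment to protocol wording. It needs no new sampling, because the rule acts on predictions and Table 4 already gives AUC24 for BID. Steady-state AUC0-24 cannot be checked directly, since the last BID dose is on the morning of Day 14, but Day 1 sampling covers the evening dose to 24 h.

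The cost is that 50 mg BID must wait for A5 at 100 mg, already planned. Under the AUC0-24 version it may then sit at the margin (about 49–50 mg BID on linear predictions) and may need a slightly lower dose or one of the optional Part A cohorts already provided for. The minimum version avoids that: 100 mg/day would be allowed once 100 mg had been given without safety concerns.
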